### 7.3.8 Central Nervous System

Retinoid use has been associated with a number of cases of benign intracranial hypertension (also known as pseudotumor cerebri), some of which involved concomitant use of tetracyclines.

The cases of benign intracranial hypertension were manifested with symptoms and signs such as severe headache, nausea and vomiting, and visual disturbances, and may be associated with papilledema. Headache generally occurs within 3 to 4 hours of starting therapy and remits spontaneously.

However, headache of unusual characteristics (eg, severity, location, pattern) to the subject should lead to contacting the Investigator. In case of such headache, it is at the discretion of the Investigator to refer subjects receiving palovarotene treatment for neurological and/or ophthalmological examination to rule out benign intracranial hypertension. Headache will be assessed using the standard AE severity scale (see [Section 9.1](#)).

### 7.3.9 Hearing and Visual Disturbances

Hearing loss is a common finding in individuals with FOP. In Study PVO-1A-001 (NHS), 42% of subjects (48 of 114) reported hearing loss at baseline. However, impaired hearing also has been reported in subjects taking retinoids. Thus, hearing tests will occur at baseline (or at

Month 6, or the next possible visit, if they were not obtained at screening) and at Months 12 and 24 in Part A, Months 36, and 48 in Part B, and Part A or B EOT/EOS (excepting Part C).

Hearing will be assessed with age-appropriate audiometry behavior testing. The assessments will determine auditory thresholds in response to speech and frequency-specific stimuli presented through earphones. In addition, The Investigator should refer subjects receiving palovarotene treatment who experience tinnitus or hearing impairment to specialized care for further evaluation. The subject with a confirmed diagnosis of hearing impairment (felt to be related to the study drug) should be discontinued from treatment, based on a benefit-risk assessment.

An ophthalmological examination should be carried out in all subjects receiving palovarotene treatment who are experiencing unexplained visual difficulties.

Corneal opacities have occurred in subjects receiving retinoids and were reversible upon drug discontinuation. Subjects receiving palovarotene treatment with corneal opacities should be assessed by an ophthalmologist.

Decreased night vision has been reported during retinoid therapy. The onset in some subjects can be sudden; therefore, subjects receiving palovarotene treatment should be informed and warned to be cautious when driving or operating vehicles at night.

### **7.3.10 Teratogenicity**

Palovarotene must not be used by female subjects who are or may become pregnant. There is an extremely high risk that severe birth defects will result if pregnancy occurs while taking palovarotene in any amount, even for short periods of time. Potentially any fetus exposed during pregnancy can be affected. There are no accurate means of determining whether an exposed fetus has been affected.

Birth defects that have been documented following exposure to retinoids include abnormalities of the face, eyes, ears, skull, central nervous system, cardiovascular system, and thymus and parathyroid glands. Cases of IQ scores less than 85 with or without other abnormalities have been reported. There is an increased risk of spontaneous abortion, and premature births have been reported.

Documented external abnormalities with other retinoids include: skull abnormality; ear abnormalities (including anotia, micropinna, small or absent external auditory canals); eye abnormalities (including microphthalmia); facial dysmorphia; and cleft palate. Documented internal abnormalities with other retinoids include: central nervous system abnormalities (including cerebral abnormalities, cerebellar malformation, hydrocephalus, microcephaly, cranial nerve deficit); cardiovascular abnormalities; thymus gland abnormality; and parathyroid hormone deficiency. In some cases, death has occurred with other retinoids with certain of the abnormalities previously noted.

## 7.4 Efficacy Assessments

### 7.4.1 Low-Dose, Whole Body Computed Tomography

All subjects will undergo a low-dose, WBCT scan (excluding head) every 6 months in Part A (Months 6, 12, 18, and 24) and annually in Part B (Months 36 and 48), Part A or B EOT/EOS and Part C (Y1 and Y2 or SC post last dose of study treatment). Of note, the last low-dose, WBCT scan (excluding head) from the NHS will be used as the baseline assessment for those subjects enrolling from the NHS as long as the scans were performed within 1 month of Screening/Study Day 1. The last low-dose, WBCT scan (excluding head) from Study PVO-1A-202 or Study PVO-1A-204 will be used as the baseline assessment for those subjects on chronic treatment enrolling from Phase 2, as long as the scans were performed within 6 months of Study Day 1. All other subjects (ie, subjects who will start chronic treatment during Study PVO-1A-301) will undergo a low-dose, WBCT scan (excluding head) at Screening/Study Day 1.

Interpretation of the CT scan will document the absence or presence of HO across various body regions, volume of total body HO, presence and volume of new HO at follow-up visits, and spinal health. All images will be interpreted by a central imaging core laboratory using standardized procedures detailed in an imaging charter.

### 7.4.2 FOP-Physical Function Questionnaire

On clinic days when multiple assessments are to be performed, the age-appropriate FOP-PFQ and the age-appropriate PROMIS Global Health Scale should be completed (in that order) by the subject/parent before any other procedures are completed on those visit days.

To evaluate the effect of palovarotene on physical function, age-appropriate forms of the FOP-PFQ will be administered at Screening and every 6 months in Part A (Months 6, 12, 18, and 24), Part B (Months 30, 36, 42, and 48), and Part A or B EOT/EOS for each subject.

The adult form of the FOP-PFQ will be completed by subjects 15 years of age and older (see [Appendix 2A](#)). Three Pediatric FOP-PFQ (FOP-PFQ-P) forms will be utilized in subjects under the age of 15 years: a self-completed form developed for 8- to 14-year-olds (see [Appendix 2B](#)), a proxy-completed form developed for 5- to 14-year-olds (see [Appendix 2C](#)), and a proxy-completed form developed for 2- to 4-year-olds (see [Appendix 2D](#)).

Study personnel will be trained on the administration of the instruments and subjects (and parents of subjects under the age of 15 years) will be provided specific instructions on how to complete the instrument independently.

### 7.4.3 PROMIS Global Health Scale

To evaluate the effect of palovarotene on physical and mental health in subjects  $\geq 15$  years of age, and mental health in subjects  $< 15$  years of age, age-appropriate forms of the PROMIS Global Health Scales will be administered at Screening and every 6 months in Part A (Months 6, 12, 18, and 24), Part B (Months 30, 36, 42, and 48), and Part A or B EOT/EOS for each subject.

The adult form of the PROMIS Global Health Scale will be administered to subjects 15 years of age and older (see [Appendix 8A](#)). Two PROMIS Pediatric Global Health Scale forms will be utilized in subjects under the age of 15 years: a self-completed form developed for 8- to 14-year-olds and a proxy-completed form developed for subjects under the age of 15 years (see [Appendix 8B](#) and [Appendix 8C](#), respectively).

Study personnel will be trained on the administration of the instruments and subjects (and parents of subjects under the age of 15 years) will be provided specific instructions on how to complete the instrument independently.

#### **7.4.4 Cumulative Analogue Joint Involvement Scale**

Range of motion will be assessed by the Investigator using CAJIS (see [Appendix 1](#)) at Screening and every 6 months in Part A (Months 6, 12, 18, 24), Part B (Months 30, 36, 42, and 48) and Part A or B EOT/EOS for each subject. The CAJIS should be assessed by the same Investigator at each time point. All Investigators will be trained to administer the CAJIS prior to subject enrollment.

#### **7.5 Pharmacokinetics**

Pharmacokinetics of palovarotene dosing will be assessed at the first 3-month safety assessment during chronic-based treatment; if samples cannot be obtained during the first 3-month safety assessment, then they can be obtained during any subsequent 3-month safety visit in the first 24 months (ie, in Part A).

Pharmacokinetics will also be assessed twice during flare-up dosing: once during the 20-mg regimen at any time between Study Days 4 to 28, and once during the 10-mg regimen at any time between Study Days 32 and 84, for the first treated flare-up only. If this is not possible for the first treated flare-up, pharmacokinetic blood samples can be obtained during any subsequent flare-up dosing in the first 24 months (ie, in Part A). Pharmacokinetic blood samples will be collected at predose and 3, 6, 10, and 24 hours post-dose.

The following parameters will be determined where possible by model independent analysis using WinNonlin™:  $C_{max,ss}$ ,  $C_{min,ss}$ ,  $T_{max,ss}$ ,  $AUC_{0-24ss}$ ,  $\lambda_z$ ,  $t_{1/2z}$ , and CL/F.

The determination of palovarotene plasma concentrations will be performed using a validated LC-MS/MS method, and exploration of any relationships with palovarotene exposure will be performed. The time of sample collection as it relates to the time of dosing on the PK days will be recorded.

Detailed instructions for collection, storage, labeling, and shipment of all samples will be provided in the Laboratory Manual.

#### **7.6 Genotyping**

On Screening/Study Day 1, a blood sample will be collected and the ACVR1 gene-coding region will be sequenced by a central genotyping laboratory to assess for the presence of an FOP-associated mutation of the ACVR1 gene for new subjects or for subjects who have not undergone previous genotyping as part of Study PVO-1A-001. Subjects enrolling from Study

PVO-1A-202 or Study PVO-1A-204 do not need to undergo repeat genotyping. Any subject enrolled who does not have an ACVR1 mutation known to be associated with FOP will be discontinued. If the Investigator has any reason to believe a subject does not possess an FOP mutation, enrollment may be delayed until the genotype is confirmed.

### 7.7 Data Monitoring Committee

A Data Monitoring Committee (DMC) will be established to review safety information periodically and on an ad hoc basis as outlined in the DMC Charter, which is maintained separately from the study protocol. The DMC can recommend temporary or permanent stopping of the study at any time if there are significant safety concerns. The DMC Charter includes recommended safety stopping rules. The DMC will also review the results of pre-planned interim analyses (see Section 8.7). In addition to the Investigator, the DMC will make recommendations for potential dose modifications in the event of treatment-related adverse bone effects as described in the Bone Safety Management Plan.

The DMC will include members with relevant clinical expertise, including a good understanding of the safety of retinoids. The methodology and the operating procedures for the safety reviews will be developed by the Chairperson in collaboration with the sponsor and will be documented in the DMC Charter.

### 7.8 Temporary Measures (Procedures Related to COVID-19 Pandemic)

#### **Procedures related to COVID-19 pandemic**

Temporary measures put in place for the conduct of Study PVO-1A-301 (MOVE study) during the COVID-19 pandemic will continue until such time as the situation resolves, at which point the protocol assessments will return to those specified. Investigators will determine the feasibility of dosing on a subject-by-subject basis, depending on the ability to conduct safety monitoring and providing subjects an adequate supply of study drug, in accordance with local requirements. These recommendations will remain in place for as long as the COVID-19 pandemic warnings are in effect in territories participating in the trial. The timing of when the pandemic is declared over may vary on a country-by-country basis as well as between sites in the same country, and as such the temporary measures may remain in place for differing periods of time per country/site.

The study visits and assessments to be conducted during this period are listed below:

#### **Study Visits and Assessments**

- 1) **For subjects aged under 14 years that are still participating in the study but not currently receiving palovarotene treatment as per the global partial clinical hold or for any other reason**, they will complete Part A or B EOT/EOS and be invited to participate in Part C and undergo assessments outlined in [Table 3](#).
- 2) **For subjects aged 14 years and older who are being considered for re-starting palovarotene treatment but have NOT yet re-started**, the following minimum assessments are to be done via remote monitoring (video conference/phone calls) by the Investigator (or delegated study staff):

- a. Chronic visits every 3-6 months (per protocol): assess for childbearing status (females only) and pregnancy prevention measures, CAJIS, ConMeds, adverse events, review subject diary, PROMIS Global Health Scale\*, FOP-PFQ\* (\*assessments that can occur remotely but are not required as these are not essential to ensure subjects' safety).
- b. For females of childbearing status: if pregnancy testing did not continue monthly per protocol post the study medication interruption then at a minimum a self-administered urine pregnancy test is to be done within 4 weeks before re-starting palovarotene treatment.
- c. All subjects should have laboratory assessments (hematology, biochemistry, urinalysis) within 4 weeks before re-starting palovarotene treatment.
- d. All subjects who were skeletally immature at the last assessment will have a hand-wrist and knee radiographs within 12 weeks before re-starting palovarotene treatment. For on-treatment subjects who have not reached at least 90% skeletal maturity radiograph assessments should continue per protocol either on site or remotely.

Site staff will also assess the subject's ability to restart remotely.

- 3) **For subjects 14 years and over that plan to reinitiate dosing, once dosing is reinitiated following the required approvals for restart (Ethics Committee and Competent Authority), the following minimum assessments that cannot be performed via remote monitoring must be performed either at the clinical site, at the subject's home (by Symphony nursing) or at a local medical facility in order for the Investigator to adequately monitor the safety of subjects:**
  - a. Via remote monitoring (telephone or video conferencing) by Investigator (or delegated study staff):
    - i. Chronic visits (per protocol schedule every 3 and/or 6 months): C-SSRS, assess for childbearing status (females only) and pregnancy prevention measures, CAJIS, ConMeds, adverse events, PROMIS Global Health Scale\*, FOP PFQ\* (\*assessments that can occur remotely but are not required as these are not essential to ensure subjects' safety), study drug dispensing
    - ii. Flare up visits (per protocol schedule): C-SSRS, ConMeds, adverse events, study drug dispensing
  - b. Via home visit by Symphony nursing/local assessment
    - i. Chronic visits per protocol schedule (every 3 and/or every 6 months): body weight, vital signs, hematology, biochemistry, urinalysis, self-administered pregnancy test (monthly), ConMeds, adverse events, review subject diary
    - ii. Flare up visits (per protocol schedule): vital signs, body weight, hematology, biochemistry, urinalysis, self-administered pregnancy testing, ConMeds, adverse events, review subject diary
- 4) **Based on the known safety profile of palovarotene to date in FOP patients, the following assessments can be postponed as determined by the Sponsor and individual site Investigators, as they do not constitute assessments where a safety**

**concern has been raised.** The below assessments were also deemed acceptable to postpone by the DMC chair.

- a. To date low dose whole-body CT has not indicated a safety concern of avascular necrosis of the hip. Any concerns for avascular necrosis of the hip based on clinical assessment should be followed up;
- b. For subjects who have reached at least 90% skeletal maturity radiograph assessments may be postponed given the low risk of early growth plate closure as well as growth plate abnormalities;
- c. Linear height and knee height (Subjects 14 years and older are at or near adult height indicated by skeletal maturity of at least 90%);
- d. ECG (FOP patients can have ECG abnormalities, ECG changes noted in subjects on Palovarotene were similar to those seen in the untreated subjects in the Natural History Study. Clinical concerns of abnormal ECG findings should continue to be followed);
- e. Hearing evaluation (As a class, retinoids can cause abnormal hearing. Evaluation should be performed if there is clinical concern);
- f. Physical exam (Palovarotene has been shown to cause retinoid skin reactions which can be assessed remotely);

Individual subjects may require assessments if there is a clinical concern as identified by the Investigator. Protocol deviations that have an impact on subject safety should be notified immediately to CRO/Sponsor as it may necessitate an urgent safety measure notification to competent authorities and ethics committees in some countries.

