
Location/Section Number	Change	Rationale

Synopsis                      Section 3.1 Overview of the Study Design                      Section 3.2 Study Rationale                      Section 5.1 Study Population
	
As of 04Dec2019 all subjects < 14 years of age were required to interrupt study drug due to a partial clinical hold placed on the palovarotene clinical development program by the US FDA. Treatment will subsequently not be restarted in children <14 years of age.
	
As a consequence of the FDA partial clinical hold subjects remained off treatment for a prolonged period of time. As such a significant gap in dosing occurred which would render any further data to inform additional benefit/risk uninterpretable in this patient population. Part C was added to ensure continued collection of safety data off treatment for these subjects and any subjects who stopped treatment for any other reason.

Section 7.3.3 Bone Safety Management Plan                      Section 7.4.1 Low-dose, Whole Body Computed Tomography
	
Added assessments for spinal health carried out on low dose WBCT scans collected in the study.
	
Emerging data from PVO-2A-201 trial in the multiple osteochondroma indication has suggested a potential effect of PVO on bone mineral accrual. As such assessments were added to further characterize this risk in FOP subjects.

Section 3.1 Overview of Study Design                      Section 7.1 Screening, Recruitment, and Informed Consent                      Section 7.8 Temporary Measures (Procedures Related to COVID)
	
Integrated protocol amendment 4 addendum previously created to describe temporary measures applied during the COVID pandemic. Additional update to these temporary measures to clarify that radiographic assessments are required for subjects (who were skeletally immature at their last assessment) as part of the minimal safety procedures prior to re-initiation of palovarotene.
	
To integrate protocol amendment 4 addendum. To assess skeletal maturity in subjects ≥14 years re-initiating treatment in order to ensure appropriate safety follow up as well as determine if weight-based dosing is required.

Other changes that did not affect the clinical conduct of the study:
		

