 At Screening, subjects under the age of 18 years will undergo knee (AP view) and hand-wrist radiographs (PA view, preferable on the left side) to determine whether they have open epiphyseal growth plates and to assess the distal femoral angle; they will also undergo standardized measurements of linear and knee height. (Subjects enrolling from the NHS or the Phase 2 studies that underwent knee and hand-wrist radiographs within 1 month of Screening will not need to have radiographs repeated at Screening.) Those subjects found to be skeletally immature will continue knee and hand-wrist radiographs, and linear and knee height measurements (all in triplicate) at Months 6, 12, 18, 24, 30, 36, 42, and 48. Limb/joint AEs in these subjects will be evaluated by any clinical and radiographic assessments deemed appropriate by the Investigator. Once a subject has achieved 100% skeletal maturity (confirmed by radiography and defined by growth plate closures), knee and hand-wrist radiographs will no longer be required. In addition, once a subject is 18 years old, linear and knee height growth assessments will no longer be required. If 100% skeletal maturity is not achieved at both locations, then only the location that is still maturing would need to be monitored.

 Knee and hand-wrist radiograph assessments will be performed at Months 3, 9, 15, 21, 27, 33, 39, or 45 (±2 weeks) in those subjects who (1) received flare-up dosing in the period of time since their last assessment; and (2) had not achieved 100% skeletally maturity on their last assessment. These radiographic assessments will be conducted at the clinical site unless the Investigator determines they can be performed at a local medical facility. All assessments will be performed at the clinical site if the radiographs cannot be performed locally.

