### **7.2.3 Body Weight and Linear Growth Assessments**

All subjects will have body weight assessed at Screening and every 3 months in Part A (Months 3, 6, 9, 12, 15, 18, 21, and 24) and Part B (Months 27, 30, 33, 36, 39, 42, 45, and 48), Part A or B EOT/EOS and Part C (Years 1 and 2 or SC post last dose of study treatment).

For subjects receiving flare-up-based treatment in Parts A and B, body weight will also be recorded at Flare-up Cycle Safety Day 1 and every 12 weeks thereafter during safety assessments until treatment of the last flare-up or traumatic event in the flare-up cycle is completed.

Subjects 18 years of age and older will have linear growth assessed by stadiometer at Screening in Part A. Subjects under the age of 18 years enrolled with open epiphyseal growth plates will

have linear growth assessments (in triplicate) by stadiometer and knee height measurements (in triplicate) at Screening and every 6 months (Months 6, 12, 18, and 24). Once a subject is 18 years old, triplicate linear growth and knee height assessments will no longer be required. The 6-month assessments of linear growth in subjects under the age of 18 years will continue in Part B (Months 30, 36, 42, and 48), Part A or B EOT/EOS and Part C (Years 1 and 2 or SC post last dose of study treatment)

Linear growth measurements will be performed by trained and qualified study personnel at the same time of day for each assessment, if possible. The stadiometric measurement instructions will include practices that reduce measurement error including calibration of equipment, proper subject positioning, and measurement capture. The same examiner should be used whenever possible to standardize the performance of procedures and minimize the inter-examiner variability. Measurement of knee height will also be standardized.

In addition, the length of bilateral tibia and femur will be assessed by WBCT scan every 6 months up to Month 24 in Part A; and annually up to Month 48 in Part B; and annually in the NHS.

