**5) End of Treatment/End of Study Assessments:**

- a. The following assessments should be performed via remote monitoring (telephone or video conferencing) by Investigator (or delegated study staff):
  - i. C-SSRS, assess for childbearing status (females only) and pregnancy prevention measures, CAJIS, Con-Meds, adverse events, PROMIS Global Health Scale, FOP PFQ
- b. The following assessments should be performed at the subject's home (by Symphony nursing) or at a local medical facility: Body weight, vital signs, hematology, biochemistry, urinalysis, pregnancy test (monthly), ConMeds, adverse events, review subject diary

**6) Once on-site visits resume, the following assessments should be performed on site as well as any assessment that was not obtained via remote monitoring or Symphony nurse:**

- a. X-rays, Whole-Body CT, Linear and Knee Height, Physical Exam, Hearing Test, ECG.

**7) Informed Consent/Subject Communication:** In consultation with their site IRB/EC, Investigators are required to inform subjects of the temporary changes (during the COVID-19 global pandemic) to the study conduct and monitoring plans that could impact them and their willingness to continue participation in the trial. The method of communication to subjects (e.g., email, phone call, information letter) and documentation of subject/caregiver acknowledgement is to be performed and

documented in accordance with local regulations/EC requests and guidance. All contacts with subjects must be filed in the source records.

A risk mitigation assessment will be performed for each subject at the site in order to determine how their participation may be impacted. Sites must ensure that appropriate measures are taken to ensure the safety of FOP subjects in light of the ongoing COVID-19 pandemic, taking into consideration local Ethics Committee and Competent Authority guidance, as well as the ability of individual Investigators and sites to adequately monitor subject safety.

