Hearing was assessed via age-specific pure tone audiogram monitoring via baseline and follow-up age-specific hearing evaluation tests. A listing will summarize by-subject results.

Pregnancy and Teratogenicity Assessment

Pregnancy and pregnancy outcomes were monitored throughout the study. A listing will summarize by-subject results.

Bone Safety Assessments

Two events led to a prolonged treatment interruption period. The first interruption occurred following a partial clinical hold issued by the US Food and Drug Administration (FDA) on the 4 December 2019 for subjects under 14 years of age in palovarotene clinical studies due to the identification of the risk of PPC. The second interruption occurred following the outcome of the PVO-1A-301 second interim analysis that crossed the threshold for futility, which resulted in the per-protocol treatment discontinuation of subjects ≥ 14 years of age on 24 January 2020.

Bone safety data will be described for following time periods:

The Original Baseline Period

The original baseline period will be defined by the original baseline through February 2020.

The Interruption (Off-treatment) Period

The baseline for the off-treatment period is the earlier of the first assessment while off-treatment or the assessment within 1 month prior to the last dose of palovarotene. Bone growth assessments during the interruption period included subjects in the off-treatment population, which was defined as subjects < 18 years of age at first study entry who interrupted palovarotene after the clinical hold date and did not re-initiate treatment and who had an off-treatment baseline and post-off-treatment baseline visit.

The end of the interruption period occurred either at the end-of-treatment/end of study visit if the subject discontinued from the study, at the end-of-study visit if they completed the study, at the new baseline if the subject re-initiated palovarotene treatment.

The New Baseline Period

A new baseline was established by the re-initiation of palovarotene dosing following the interruption period. New baseline bone growth assessments includes all subjects who had a new baseline and a post-new baseline visit and received at least one dose of palovarotene after the new baseline visit date. The new baseline visit date was defined as the date of the last visit prior to the re-initiation of palovarotene treatment following the interruption period.

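### Protocol Section 7.8 item 4c lets height be postponed with no maturity condition, although items 2d and 4b allow for restarters aged 14 or older who are below 90% skeletal maturity

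*Protocol*

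**What the plan says.** Protocol Section 7.8 sets temporary rules for the pandemic period. Its item 4 lists assessments that the sponsor and Investigators may postpone. Two entries matter here.

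- Item 4b, radiographs: "For subjects who have reached at least 90% skeletal maturity radiograph assessments may be postponed given the low risk of early growth plate closure".
- Item 4c, height: "Linear height and knee height (Subjects 14 years and older are at or near adult height indicated by skeletal maturity of at least 90" percent.

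Item 2 covers subjects of 14 or over who are being considered for restart. Item 2d requires hand-wrist and knee radiographs in the 12 weeks before restart for anyone skeletally immature at the last assessment. It then adds: "For on-treatment subjects who have not reached at least 90% skeletal maturity radiograph assessments should continue per protocol either on site or remotely".

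The ordinary schedule treats the two measures as a pair. Table 1, footnote 6: "Those subjects found to be skeletally immature will continue knee and hand-wrist radiographs, and linear and knee height measurements (all in triplicate", at each six-monthly visit.

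Once on-site visits resume, item 6a lists what is then to be done on site: "X-rays, Whole-Body CT, Linear and Knee Height, Physical Exam, Hearing Test, ECG".

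**The concern.** Item 4c uses age 14 as a stand-in for 90% maturity and postpones height on that basis. For a restarter of 14 or over who is below 90%, the stated reason does not apply, yet the permission does.

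These are the subjects in whom growth still matters. Protocol Section 3.2 calls premature physeal closure a serious identified risk, and Section 1.1.3.2.3 says it has been seen at all ages, although the effect on growth is likely to be larger in the youngest. Item 4 justifies its list on the ground that no safety concern has been raised for these assessments. That is hard to apply to linear growth in a subject with open growth plates who is back on drug.

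A radiograph shows the state of the growth plate; height and knee height show how much the subject has grown. The other length measure, femur and tibia length from whole-body CT (Section 7.2.3), does not reliably fill the gap, because item 4a puts CT on the same postponable list.

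**Working it through.** The plan gives no figure to reproduce. The check sets the relevant items side by side.

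1. **Who is affected.** Treatment is not restarted under age 14 (Section 3.1), and item 1 of Section 7.8 sends those subjects to Part C, whose Table 3 includes linear and knee height. The on-treatment subjects to whom item 4c applies are therefore 14 or older. Table 1, footnote 6 ends height measurement at 18. The premise of item 4c fails only below 90% maturity. The affected group is restarters aged 14 to under 18 and below 90%.

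2. **Whether the section accepts that this group can exist.** Item 2d stands under a heading for subjects of 14 or over and gives an instruction for on-treatment subjects below 90%. If everyone of 14 or over were at 90% or more, that instruction would apply to nobody. Item 4b's condition would also be unnecessary for restarters. The dosing rule in Section 3.1 (text before Table 4) treats maturity below 90% as possible at any age under 18. The Amendment 5 rationale points the same way: maturity is to be assessed "in subjects ≥14 years re-initiating treatment in order to ensure appropriate safety follow up as well as determine if weight-based dosing is required". Weight-based dosing applies only below 90%. That rationale is supporting context; the inconsistency stands on items 2d, 4b and 4c alone.

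3. **What each measure gets in Section 7.8.**

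| Maturity | Radiographs | Linear and knee height |
|---|---|---|
| 90% or more | may be postponed (4b) | may be postponed (4c) |
| below 90% | continue (2d) | may be postponed (4c) |

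The lower right cell is the inconsistency. The base schedule would have both measures continue there.

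4. **Whether item 4c's parenthesis is itself a condition.** Item 4b opens by naming the subjects to whom it applies. Item 4c names the assessment and then asserts something about all subjects of 14 or over. As worded it is a reason, not a restriction. If a restriction was meant, the text needs to say so.

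5. **Length of the delay.** Heights are due every 6 months in Table 1. If one is postponed to the next scheduled visit, the interval is 6 + 6 = 12 months, before visit windows of ±1 month. It is shorter if on-site visits resume sooner.

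**The case against.** The best defence is that radiographs and height deserve different treatment in a pandemic. The identified risk is closure of the growth plate, and radiographs detect it directly. Section 6.5 lets the Investigator act on closure whether or not growth has slowed. Radiographs can be done at a local facility, while stadiometry is harder to move: "Linear growth measurements will be performed by trained and qualified study personnel at the same time of day for each assessment, if possible", with calibrated equipment and triplicate readings. The DMC chair accepted the postponements. This defence stands as a reason not to require extra visits for height. It does not repair a permission whose stated reason is untrue for the subjects item 2d describes.

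Stronger readings are tempting, and the documents do not support them.

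- A reader might infer that height was waived. Item 4 is permissive. Section 3.1 says that, despite the addendum, assessments not done per protocol were to be reported as deviations. Section 7.8 calls for a risk assessment for each subject and lets Investigators add assessments for clinical concern. Item 6a restores height.
- A reader might see significance in height being absent from the minimum lists in items 2, 3 and 5. Items 2a and 3a are telephone or video lists, and items 3 and 5 omit radiographs too, although item 2d continues them below 90%.
- A reader might infer that the growth analysis after restart loses its starting value, because SAP Section 2.4.5 says "The new baseline visit date was defined as the date of the last visit prior to the re-initiation of palovarotene treatment". The SAP does not say that this visit is remote or lacks a height. Its Sections 1.10.2 and 2.4.4 say assessments were to continue during the dosing interruptions, and growth velocity is annualised by the actual days between heights.

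**Conclusion.** Item 4c is wrong as written, at minor weight. It rests on a premise about age and maturity that items 2d and 4b of the same section do not share, and nothing elsewhere in the protocol or SAP resolves the difference. The consequence is a discretionary delay in height and knee height for restarters aged 14 to under 18 who are below 90%. Their number is not stated and may be small. Growth-plate radiographs are kept for them throughout.

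The conclusion assumes that item 4c's parenthesis is a justification and not an unstated condition. If a condition was intended, the defect is one of wording only and the same edit cures it. The documents do not show how many heights were in fact postponed, and no claim is made about that.

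**What to change.** Make two wording changes in Protocol Section 7.8.

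- **Item 4c:** allow linear and knee height to be postponed only in subjects whose most recent hand-wrist radiograph shows skeletal maturity of 90% or more. This matches item 4b.
- **Item 2d:** add that subjects below 90% have triplicate linear and knee height taken at the radiograph visits already required, when those visits are on site or at a facility that can meet Section 7.2.3; otherwise at the first on-site visit.

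The fallback is what item 6a already provides. What is gained is that, where a proper measurement is feasible, it becomes a requirement instead of an option for the subjects still growing. No visit is added solely for height. The cost is two sentences and some extra measurements at visits that take place anyway.
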